4.4 Specimen collection, processing, storage and analysis

For each participant, ~2.5 ml of blood will be collected at each timepoint at baseline (Day 1), and on day 5 prior to administration of intravaginal artesunate (time 0), and at 15, 30min, 1h, 3h, and 6h after administration. Blood will be collected in gold/yellow top tubes and centrifuged to plasma which will be stored at -80°C until analyzed. Samples will be stored at Kenya Medical Research Institute (KEMRI)-affiliated accredited laboratories in Kisumu, Kenya, with cold chain maintained from collection to storage until shipping for analysis. All study staff as well as laboratory staff will be trained on study SOPs.

DHA and artesunate plasma testing: Specimens will be tested at the Walter Reed Army Institute of Research, (WRAIR) Division of Experimental Therapeutics laboratory in Maryland, USA which has validated DHA and artesunate assays. Analysis will be led by [name], D.O Chief of Clinical at the Walter Reed Army Institute of Research and the Clinical Pharmacology Fellowship Program Director. Plasma samples will be shipped under cold chain and remain frozen at at -80°C in WRAIR laboratory facilities until ready for analysis. Analysis will be performed using a validated high-performance Liquid Chromatography Mass Spectrometry (LCMS) assay at WRAIR with limits of quantification of Artesunate and DHA of approximately 80nM and 70 nM, respectively. 31,71 Quality control (QC) samples will be included with each assay batch, with a requirement that the run is acceptable only if the QC is within +/-15% of the nominal value. 35 The WRAIR Division of Experimental Therapeutics, Drug Metabolism and Disposition has over 75 years' experience with drug and product development, having achieved U.S FDA approval of 9 malaria drugs and more than 65 investigational new drug applications. All appropriate material transfer agreements and shipping licenses will be obtained from all relevant regulatory bodies including the Amref ESRC before specimen shipping is done. All specimens will be destroyed following testing. Each sample will be assigned a unique code number, and no identifiable personal health information (PHI) will be on the specimen label.

Pharmacokinetic analysis: Conventional pharmacokinetic parameters - AUC (0, infinity), half-life, apparent clearance, the volume of distribution, maximum plasma concentration (Cmax), time to Cmax will be determined from the plasma concentration-time data using noncompartmental analysis. Peak plasma concentration (Cmax) and time to reach peak concentration (tmax) for artesunate and DHA will be the observed values. The AUC of AS will be calculated by linear trapezoidal summation with extrapolation to infinity. With respect to

DHA, AUC will be calculated to the last drug measurable time point. The elimination rate constant (β), will be calculated from the slope of the terminal phase of the log concentration-time profile, and the elimination half-life (t1/2) calculated from the ratio of ln 2/ β . Other PK parameters will be calculated using standard model-independent formulae.³⁹ The estimates of PK parameters for DHA will assume complete conversion of AS to DHA as reported previously.³⁵ Data will be plotted graphically and analyzed using statistical software. Data will be presented as mean with standard deviation (SD).

Compliance Statement: Biospecimen collection for this study will be conducted in full accordance with all applicable University of North Carolina (UNC) Research Policies and Procedures including Good Clinical Practice (CGP) policies, and all applicable Federal and state laws and regulations including 45 CFR 46, and the Health Insurance Portability and Accountability Act Privacy Rule, as well as the in-country regulatory agencies including the Amref Ethics and Scientific Review Committee (ESRC), the Kenya Pharmacy and Poisons Board (PPB), the National Commission for Science, Technology & Innovation (NACOSTI) and any other regulatory bodies required in-country. Any episode of noncompliance will be documented. The investigators will perform the study in accordance with this protocol, will obtain consent, and will report unexpected problems in accordance with the UNC IRB Policies and Procedures and all federal requirements. Collection, recording, and reporting of data will be accurate and will ensure the privacy, health, and welfare of research participants during and after the study.

Biosafety: To ensure the safety of our research staff, study participants, and the surrounding community, we will follow the biosafety level 2 (BSL-2) standard as per the Kenyan Laboratory Biosafety and Biosecurity Policy Guidelines and Kenya National Guidelines for Safe Management of Health Care Waste. This standard is designed to reduce or eliminate exposure of laboratory workers, other persons, and the outside environment to potentially hazardous or detrimental materials. The study drug (artesunate) is a well-characterized drug that has been extensively studied and is not known to cause disease in healthy individuals. The biological material handled, and biological waste generated during the study are moderate-risk infectious agents and pose a moderate individual risk and low community risk of exposure. By following these guidelines, we can ensure that all our procedures are conducted safely, and that medical waste is disposed of properly.

Monitoring/Data and Safety Monitoring: The Principal Investigator will provide continuous monitoring of participant safety in this trial with periodic reporting to the Data and Safety Monitoring Committee (DSMC). Meetings/teleconferences will be held at a frequency dependent on study accrual. These meetings will include the investigators as well as study coordinators, data coordinators, regulatory associates, and any other relevant personnel the principal investigators may deem appropriate. At these meetings, the research team will discuss all issues relevant to study progress, including enrollment, safety, regulatory, data collection, etc.

The team will produce summaries or minutes of these meetings. These summaries will be available for inspection when requested by any of the regulatory bodies charged with the safety of human participants and the integrity of data including, but not limited to, the oversight of Office of Human Research Ethics Biomedical IRB.

The UNC PI will be responsible for submitting the following information for review: 1) safety and accrual data including the number of participants treated; 2) significant developments reported in the literature that may affect the safety of participants or the ethics of the study; 3) preliminary response data; and 4) summaries of team meetings that have occurred since the last report. Findings of the DSMC review will be disseminated by memo to the UNC PI, the UNC IRB, and all Kenya regulatory bodies governing the study.

Removal of Participants from the Study: Any participant who does not wish to participate in the study will be exited from the study at any time they prefer. Additionally, participants who fail to adhere to significant protocol requirements, including failure to meet inclusion/exclusion criteria, use of prohibited concomitant medications, incident pregnancy, or other reasons that in the opinion of the Principal Investigator may affect participant safety may be removed from the study. The Investigator will determine if a protocol violation results in withdrawal of a participant. All protocol violations will be reported to the relevant governing IRBs.

Participants who permanently discontinue study product and follow-up prior to study completion will be asked to complete an early withdrawal visit, if willing, during which any AEs will be assessed. If study removal occurs due to pregnancy, participants will be referred to the nearest preferred prenatal facility for pregnancy care.

Replacement of Participants: A sample size of N=12 participants are needed for the primary aims of PK analysis. To allow for potential drop offs or incomplete evaluation, up to N=16 participants will be consented and enrolled to have a sample size of N=12 fully evaluable participants, who will finish all study visits and have all specimens collected. Once the minimum sample size of N=12 of fully eligible participants is met, no additional participants will be enrolled or initiate study procedures.

 Participant Withdrawal: If a participant decides to withdraw from the study (and not just from protocol therapy) an effort should be made to complete and report study assessments as thoroughly as possible. At the time of withdrawal, the investigator should attempt to establish as completely as possible the reason for the study withdrawal.

- The participant should be asked if they are willing to allow for the abstraction of relevant information from their medical record in order to meet the objectives outlined in the protocol.
- A complete final evaluation at the time of the participant's study withdrawal should be obtained with an explanation of why the participant is withdrawing from the study.
- If the participant is noncompliant and does not return for an end of study follow up assessment, this should be documented in the eCRF.
- If the reason for removal of a participant from the study is an adverse event, the principal specific event will be recorded on the eCRF.

Excessive participant withdrawals from protocol therapy or from the study can render the study un-interpretable; therefore, unnecessary withdrawal of participants should be avoided.

Participant Lost to Follow up: A participant will be considered lost to follow-up if he or she fails to return for three scheduled study visits and is unable to be contacted by the study site staff.

The following actions must be taken if a participant fails to return to the clinic for a required study visit:

- The site will attempt to contact the participant and reschedule the missed visit and counsel
 the participant on the importance of maintaining the assigned visit schedule and ascertain if
 the participant wishes to and/or should continue in the study.
- Before a participant is deemed lost to follow-up, the investigator or designee will make every
 effort to regain contact with the participant (where possible, 3 telephone calls and, if
 necessary, a home visit by the study team if permission is obtained for home visit at study
 entry, or local equivalent methods). These contact attempts should be documented in the
 participant's medical record or study file.
- Should the participant continue to be unreachable, he or she will be considered to have withdrawn from the study with a primary reason of lost to follow-up.

Off-Study Criteria: Participants will be considered off study and will no longer be followed on the protocol for any reason if any of the following criteria are met: when the participant reaches the end of the study as defined by the Schedule of Events Table, participant withdraws consent for treatment and any further data collection, death, or lost to follow-up.

1074
1075 **Malaria treatment during dosing phase (Day 1-5):** If study participants are diagnosed with
1076 malaria during the Artesunate pessary dosing phase (day 1-5), a non-ACT treatment will be used
1077 to avoid PK studies confounding. Participants will be encouraged to sleep under a mosquito net
1078 to reduce the chance of new malaria infection during the study.

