LMICs. This led to a recent Phase I study in the United States that demonstrated that selfadministered vaginal artesunate inserts (pessaries) are safe, well-tolerated, and demonstrate efficacy for treatment of CIN2/3. Based on the mechanism of action, the clinical safety profile, and widespread availability as a generic drug on the World Health Organization (WHO) List of Essential Medications, vaginal artesunate inserts (pessaries), if backed by data from randomized trials, may offer patient-controlled and access cervical precancer treatment method for women in LMICs who face the greatest burden of cervical cancer and have difficulty accessing skilled providers for precancer treatment. However, given that artesunate is a well-known drug used in malaria treatment, it is critical to ensure that vaginal application of the drug will not promote resistance for use in malaria treatment. **Objectives:** The proposed study seeks to investigate the pharmacokinetics of Artesunate (AS) and dihydroartemisinin (DHA), the active metabolite of artesunate, following intravaginal use at the dosing and frequency being studied for cervical precancer treatment. A secondary objective is to investigate safety among study participants. **Methods:** As a recent study demonstrated safety and tolerability of intravaginal artesunate among women with CIN2/3 and the safety of artesunate is well documented in numerous malaria studies, the proposed study will be conducted in female volunteers regardless of their HPV or cervical precancer disease status. In this a single arm study, blood levels of DHA and artesunate following 5 daily applications of vaginal artesunate inserts (pessaries) will be measured. A sample size of twelve participants (N=12) are needed. Up to 16 will be consented to account for drop offs. Eligible participants will self-administer artesunate vaginal inserts (pessaries) daily in the study clinic for 5 days. Participants will undergo blood a draw prior to receiving the first dose of artesunate, and on day 5 before inserting the vaginal insert, and at 15 min, 30 mins, 1, 2, 4, 6, and 8 hours after. In each patient, pharmacokinetic parameters of artesunate and DHA will be calculated via quantitative analysis of with determination of maximum concentration (Cmax), time to Cmax (Tmax), area under the plasma concentration versus time curve (AUC), apparent clearance, and elimination half-life (t1/2). **Budget:** The estimated study budget is US \$70,000.

118 119 120

121

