
III. Protocol Summary

Protocol Title	Pharmacokinetics of intravaginal, self-administered Artesunate vaginal pessaries among women in Kenya.
Study Design	Single arm study of 12 participants who will use self-administered artesunate vaginal inserts (pessaries) on 5 consecutive days with blood draws performed at baseline and on day 5 for pharmacokinetic studies.
Study Population	Women ages 18 or older meeting inclusion criteria.
Number of participants	A sample size of 12 is needed. Up to 16 participants will be consented, if necessary, to account for drop offs.
Number of sites	2

Phase of	Phase I
study (i.e.,	
Pilot, Phase	
1, etc.)	
Clinical	Blood draw at Day 1 (Visit 1), and on Day 5 (Visit 5) at 0, 15 mins, 30
Samples	min, 1h, 2h, 4h, 6h and 8 h after self-administration of 200 mg
	intravaginal artesunate pessary.
Study	3 months
Duration	
Participant	2 weeks
Duration	
Regimen or	200 mg Artesunate vaginal insert (pessary) used daily for 5 consecutive
Intervention	days

IV. Lay Summary

122 123

124 125

126

127

128

129

130

131

132

133

134

135

136 137

138

139

140

141142

143

144

145

146

147148

149

150 151

152

153

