
- which is another way malaria drugs are given to children. To help answer this question of
- whether using low dose Artesunate pessaries for treating cervical precancer can cause resistance
- 156 for malaria treatment, up to 16 female participants will be enrolled in this study. Study
- participants will use artesunate pessaries once daily for 5 days in the study clinic, and have blood
- drawn once on day 1 (prior to first pessary use), and six times on day 5 (last day of pessary use)
- to measure the artesunate drug levels in the blood. On day 5, participants will have a cannula
- placed and blood drawn from the cannula. The volume of blood drawn each time will be
- approximately 3 ml, less than a teaspoon. In comparison, when a person donates blood,
- approximately 500 ml of blood is drawn. The goal of this study is to confirm that artesunate
- pessaries can be used intravaginally for treatment of cervical precancer without creating
- resistance of the drug for treating malaria to enable studies on its use for precancer treatment.

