1.7 Problem Statement and Study Rationale (Justification)

428 429 430

431

432

433 434

435

436

Given that artesunate is a well-known drug used in malaria treatment, it is critical to ensure that vaginal application of the drug for treatment of cervical precancer will not promote malaria resistance. Thus, a study evaluating blood serum levels after artesunate vaginal inserts administration is proposed. In this study, participants will self-administer one 200 mg artesunate vaginal insert per day for 5 days. Blood serum levels of DHA and artesunate will be evaluated prior to receiving artesunate, and on day 5, before artesunate vaginal insert (pessary) use – time 0, and at 15min, 30min, 1, 2, 4, 6 and 8 hours after use to evaluate the pharmacokinetics of artesunate following intravaginal use at the proposed dose and frequency.

437 438

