2.4 Study Schema

502 503 504

505

506

507 508

Screening/Enrollment Visit

Review eligibility criteria, review and sign informed consent, introduce and discuss study requirements, urine pregnancy test, malaria antigen testing, assign unique study number, obtain baseline clinical and demographic characteristics and medical history, pelvic examination.

509510

511512

513

514

515

Visit 1/Day 1* (may be combined with Screening/Enrollment visit)

Interval medical history
Urine pregnancy test

Blood draw for baseline Artesunate/DHA testing

Self-administration of first Artesunate vaginal insert (pessary) and tampon, followed by a 30-minute observation.

Schedule Visit 2

516517518

519

520

521

522523

524

•

Visit 2-4/Day 2-4

Interval medical history
Urine pregnancy test
Review adverse events

Self-administration of Artesunate vaginal insert (pessary) and tampon

Schedule subsequent visit

525 526

527

 \forall

Visit 5/Day 5

528 Interval medical history

PI: [name] Version 1.0

529	Urine pregnancy test
530	Review adverse events
531	Blood draw before artesunate administration (time 0)
532	Self-administration of Artesunate vaginal insert (pessary)
533	Blood draw at 15 min, 30 min, 1hr, 2hr, 4 hr, 6 hr and 8 hrs after Artesunate vaginal pessary
534	insertion
535	Schedule Visit 6
536	
537	Visit 6 (within 4-10 days of Visit 5)
538	Review adverse events
539	Study exit
540	

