4 METHODOLOGY

- 4.3 Study Details and Procedures
- 683 **Study Design and Sampling**: This is a single arm, open-label Phase I, non-randomized study.
- Participants meeting the inclusion criteria will be sequentially enrolled.

685

681

- 686 **Study Population:** The study population will be up to 16 women 18 years or older living in
- Kisumu County in Kenya, in order to have 12 fully evaluable participants, our desired sample
- size. Fully evaluable participants are those who receive artesunate inserts for 5 consecutive days
- and undergo blood draws before and after receiving artesunate at all the timepoints per study
- 690 protocol. Enrollment will stop once data from 12 fully evaluable participants are obtained. No
- more than 16 participants will be enrolled.

692 693

694

695

696

697

698

699 700

Inclusion Criteria

- 1. Age 18 years or older
- 2. Negative pregnancy test at screening
- 3. Weight ≥50 Kg at study entry*
- 4. Willingness to use contraception (hormonal or barrier) during the 5-day study dosing phase if of childbearing age (less than 50 years of age)
- 5. Ability and willingness to provide informed consent
- 6. Plan to reside in the study location during the study period
- *Justification for weight criteria: A minimum body weight of 50Kg will meet the planned artesunate dosing of ≤ 4 mg/Kg for which excellent safety data is available.

702 703 704

705

706

707

708

709

710

711

712

713

701

Exclusion Criteria

- 1. Current pregnancy or breastfeeding status
- 2. History of total hysterectomy
- 3. Known allergy to Artesunate
- 4. Have a medical comorbidity that in the opinion of the investigator would interfere with study participation
- 5. Currently receiving artemisinin-based agents for malaria treatment or completed artemisinin-based treatment within the previous 3 days.*
- Male at birth
 - 7. Current use of efavirenz antiretroviral therapy
- 714 8. Positive malaria antigen test at screening
- *Based on dihydroartesunate (artesunate's active metabolite) half-life of between 0.5-1.5 hours²⁹
- 717 **Study Location:** The study will be carried out at the Lumumba Sub-County Hospital and at the Victoria Biomedical Research Institute in Kisumu, Kenya.
- Recruitment: Participants will be recruited from among women in the general population within the vicinity of the study location, including within health facilities in Kisumu County in Kenya.

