- Update locator information (if necessary)
- Review and record adverse events using a standardized questionnaire
- Perform pelvic exam as needed based on AEs described (pelvic exam for suspected grade II or worse AEs)
- Review concomitant/prohibited medications
- Draw blood (~2.5ml) before artesunate self-administration & insert peripheral cannula for subsequent blood draws
- Artesunate self-administration using an applicator, followed by tampon insertion
- Blood draws (~2.5ml each time) at 15, 30min, 1h, 2h, 4h, 6h, and 8h after artesunate self-administration.
 - Provide transport reimbursement
- 805 Schedule visit 6

806 Visit 6: Visit 6 will occur 4-10 days after visit 5

807 808

809

804

Visit 6 activities:

- Review and record adverse events since last visit using standardized questionnaire
- Perform pelvic exam and colposcopy with digital imaging
- 811 Study exit/termination
- 812 Provide reimbursement

813814

817 818

819

820

b. 4.3 Adverse Event Reporting

815 **Definitions** 816 An adverse

An adverse event (AE) is any untoward medical occurrence in a patient or clinical investigation participant administered a pharmaceutical product and which does not necessarily have a causal relationship with this treatment. An adverse event can therefore be any unfavorable and unintended sign (including an abnormal laboratory finding), symptom, or disease temporally associated with the use of a medicinal (investigational) product, whether or not related to the medicinal (investigational) product.

821 822 823

824

825

An unexpected (unlisted) adverse event is an adverse reaction, the nature or severity of which is not consistent with the applicable product information (e.g., Investigator's Brochure for an unapproved investigational product or package insert/summary of product characteristics for an approved product).

826 827 828

A serious adverse event (SAE) is any untoward medical occurrence that at any dose:

PI: [name] Version 1.0

- 829 results in death;
- 830 is life-threatening;
- * requires inpatient hospitalization or prolongation of existing hospitalization;
- results in a persistent or significant disability/incapacity; or
 - is a congenital anomaly/birth defect

833 834 835

Important medical events as assessed by medical and scientific judgment may also be considered SAEs by the investigator and should be reported in an expedited fashion.

836 837 838

839

840

841 842

843

844 845

846

847 848

849

850

851

852

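### Day 5 blood sampling is specified in two ways: six draws in section 4.4 (specimen collection), eight in the visit plan and four other places

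*Combined protocol and SAP*

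**What the plan says.** The six-draw version appears in section 4.4 (Specimen collection, processing, storage and analysis). It calls for a pre-dose sample on Day 5 and then samples "at 15, 30min, 1h, 3h, and 6h after administration". The lay summary gives a matching count without times: blood is "drawn once on day 1 (prior to first pessary use), and six times on day 5".

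The eight-draw version appears in five places:

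- Abstract, Methods: "and on day 5 before inserting the vaginal insert, and at 15 min, 30 mins, 1, 2, 4, 6, and 8 hours after".
- Protocol Summary, Clinical Samples row, which also lists time 0: "min, 1h, 2h, 4h, 6h and 8 h after self-administration of 200 mg".
- Section 1.7, after a time 0 sample: "and at 15min, 30min, 1, 2, 4, 6 and 8 hours after use to evaluate the pharmacokinetics".
- Section 2.4, Visit 5, after a pre-dose draw: "Blood draw at 15 min, 30 min, 1hr, 2hr, 4 hr, 6 hr and 8 hrs after Artesunate vaginal pessary".
- Section 4.2, Visit 5 activities, after a pre-dose draw: "Blood draws (~2.5ml each time) at 15, 30min, 1h, 2h, 4h, 6h, and 8h after artesunate".

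The Schedule of Events table marks blood draws at Visit 5 but gives no times. Under Study Population, women count as fully evaluable if they take all five doses "and undergo blood draws before and after receiving artesunate at all the timepoints per study" protocol. The paragraph on replacing participants likewise requires every specimen to be collected.

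**The concern.** All the Day 5 pharmacokinetic results come from these samples. DHA AUC, the primary endpoint, is integrated only to the last sample with measurable drug, so the list of times limits the window. Cmax and Tmax are taken as observed, so they can fall only on a listed time. The terminal slope, and through it half-life and V/F, needs enough samples after the peak.

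The two lists cannot stand in for each other. The six-draw list has nothing between 1 h and 3 h and stops at 6 h. Section 1.3 puts the DHA peak at about 2 h after oral and 1.80 h after rectal dosing. The vaginal peak time is unknown (section 1.6 says there are no such data), and a peak near 1 h or 3 h would still be caught.

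Evaluability is also left undefined. Read literally, a woman sampled on one list has missed required times on the other. A Day 5 sample that was not drawn cannot be recovered later.

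**Working it through.** **1. The lists side by side**

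| Source | Day 5 times | Draws |
|---|---|---|
| Section 4.4 (specimen collection) | 0, 15 min, 30 min, 1, 3, 6 h | 6 |
| Lay summary | count only | 6 |
| Abstract, Protocol Summary, 1.7, 2.4, 4.2 Visit 5 | 0, 15 min, 30 min, 1, 2, 4, 6, 8 h | 8 |

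Common to both: 0, 15 min, 30 min, 1 h, 6 h. Only in the eight-draw list: 2, 4, 8 h. Only in the six-draw list: 3 h.

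**2. Counts** (one Day 1 sample added; about 2.5 mL per draw, from sections 4.2 and 4.4)

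- Per woman: 8 + 1 = 9 against 6 + 1 = 7 samples.
- Volume: 9 × 2.5 = 22.5 mL against 7 × 2.5 = 17.5 mL.
- For 12 women: 9 × 12 = 108 against 7 × 12 = 84 samples.

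**3. Evaluability.** Enrolment is capped at 16 and 12 evaluable women are needed. If five were sampled on the list not used to judge evaluability, 16 − 5 = 11 could qualify. This is a hypothetical case.

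**4. Illustration of the effect on AUC and Cmax.** No vaginal data exist, so this borrows the rectal 200 mg DHA values in section 1.3: Cmax 385.6 ng/mL, Tmax 1.80 h, half-life 1.21 h, AUC 965 ng·h/mL. The quantification limit is 70 nM (section 4.4). With an assumed DHA molecular weight of 284.35, that is 70 × 284.35 / 1000 = 19.9 ng/mL. Values below it are set to zero. AUC is the linear trapezoid to the last quantifiable sample, divided by the model's AUC to infinity.

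The curve is C(t) = AUC × ka × ke / (ka − ke) × [exp(−ke(t − lag)) − exp(−ka(t − lag))], with ke = ln 2 / 1.21 = 0.573 per h. Two fits were used:

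- *Lag:* lag 1.17 h, ka 3.41 per h. It matches all four rectal values, but the lag is a fitting device with no support in the documents.
- *No lag:* ka 0.539 per h. It matches Cmax and Tmax but gives an AUC of 1,888, not 965.

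Lag fit at full rectal exposure:

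- Eight draws: 0 up to 1 h, then 373.9 (2 h), 131.4 (4 h), 41.8 (6 h), below the limit at 8 h. AUC = ½(1)(373.9) + ½(2)(373.9 + 131.4) + ½(2)(131.4 + 41.8) ≈ 865; 865 / 965 = 90%. Cmax 373.9 / 385.6 = 97%.
- Six draws: 0 up to 1 h, then 231.8 (3 h), 41.8 (6 h). AUC = ½(2)(231.8) + ½(3)(231.8 + 41.8) ≈ 642; 642 / 965 = 67%. Cmax 231.8 / 385.6 = 60%.

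No-lag fit: AUC 1,749 / 1,888 = 93% against 1,544 / 1,888 = 82%; Cmax 99% against 87%.

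AUC recovered, eight against six draws, as exposure falls:

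| Exposure relative to rectal | Lag | No lag |
|---|---|---|
| Full or half | 90% vs 67% | 93% vs 82% |
| Quarter | 72% vs 24% | 83% vs 82% |
| Tenth | 19% vs 24% | 62% vs 44% |
| Twentieth | nothing quantifiable | nothing quantifiable |

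**5. Sensitivity to peak time** (no lag, Cmax 385.6, ke fixed, ka varied; eight against six draws)

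| Tmax (h) | AUC recovered | Cmax recovered |
|---|---|---|
| 1 | 96% vs 97% | 100% vs 100% |
| 1.5 | 96% vs 89% | 96% vs 93% |
| 2 | 89% vs 77% | 100% vs 91% |
| 2.5 | 77% vs 62% | 98% vs 98% |
| 3 | 63% vs 48% | 96% vs 100% |
| 4 | 38% vs 27% | 100% vs 97% |

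The six-draw list loses AUC once the peak is at 1.5 h or later. In this family its Cmax loss is small except near a peak of 1.8 to 2 h.

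**The case against.** The strongest reply is that this is clerical. Five statements, including the visit instructions staff would follow, agree on eight draws. The exception is one sentence in a section on specimen handling, plus a bare count in the lay summary that may be a simple miscount. Staff are to be trained on SOPs that are not visible here and may be correct. That is a fair description of how the error probably arose. It does not make the text safe, because section 4.4 is the section on specimen collection and the protocol gives no order of precedence. The clinic time of six to eight hours in section 5.1 does not settle it either.

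The numerical illustration also deserves caution:

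- The lag forces the 1 h sample to zero and so penalises the six-draw list by construction.
- The no-lag fit overshoots the cited AUC.
- In the peak-time table, Tmax values of 2, 2.5, 3 and 4 h imply terminal half-lives (ln 2 / ka) of about 1.6, 2.6, 4.0 and 8.7 h, against the 1.21 h used to build the model. Part of those AUC losses is a long tail that both lists cut off.
- Section 5.4 expects little or no systemic drug. If that is right, the choice of list may matter little for AUC.

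These points stand, and they limit how far the size of the loss can be stated. The evaluability shortfall is likewise hypothetical, since nothing suggests that five women would be sampled on the other list. Neither the contradiction nor the undefined evaluability rule depends on the model.

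**Conclusion.** The concern holds and should be fixed before Day 5 sampling. The current text gives two incompatible Day 5 schedules: the six-draw list omits 2, 4 and 8 h and adds 3 h. The primary endpoint, the other PK parameters and the count of evaluable women all rest on which is used. This conclusion needs only the text.

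The effect on the results is less certain. If vaginal absorption resembled the rectal profile at full or half its exposure, the six-draw list would recover 11 to 23 percentage points less of the DHA AUC (93 − 82 and 90 − 67). At lower exposure the difference runs from a large loss through none to a small reversal, depending on the assumed profile. The figures rest on borrowed rectal values, an assumed molecular weight and a one-compartment curve.

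**What to change.** In section 4.4 (specimen collection), replace the post-dose times with those in the Visit 5 plan: 15 and 30 min, 1, 2, 4, 6 and 8 h. Correct the lay summary to eight Day 5 draws. The visit plan is the apparent intent, since it agrees with four other places, but the sponsor should confirm it because no section declares precedence.

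Then check that the SOPs and the number of draws told to participants agree. Check also the clinic time in section 5.1, because an 8 h post-dose sample plus the pre-dose procedures takes more than eight hours.

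The cost is a text correction. No draw is added beyond those already in the visit plan. The consent pages and SOPs were not available for this review, so whether they also need the change is unknown.
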